9.1 Pre-study Documentation

This study will be conducted in accordance with the ethical principles that have their origin in the Declaration of Helsinki as stated in 21 CFR §312.120(c)(4); consistent with GCP and all applicable regulatory requirements.

Before initiating this trial, the Investigator will have written and dated approval from the Institutional Review Board for the protocol, written informed consent form, subject recruitment

materials, and any other written information to be provided to subjects before any protocol related procedures are performed on any subjects.

The clinical investigation will not begin until either FDA has determined that the study under the Investigational Drug Application (IND) is allowed to proceed or the Investigator has received a letter from FDA stating that the study is exempt from IND requirements.

9.2 Institutional Review Board Approval

The protocol, the proposed informed consent form, and all forms of participant information related to the study (e.g. advertisements used to recruit participants) will be reviewed and approved by the UCSF CHR (UCSF Institutional Review Board). Prior to obtaining CHR approval, the protocol must be approved by the Helen Diller Family Comprehensive Cancer Center Site Committee and by the Protocol Review Committee (PRC). The initial protocol and all protocol amendments must be approved by the IRB prior to implementation.

9.3 Informed Consent

All participants must be provided a consent form describing the study with sufficient information for each participant to make an informed decision regarding their participation. Participants must sign the CHR-approved informed consent form prior to participation in any study specific procedure. The participant must receive a copy of the signed and dated consent document. The original signed copy of the consent document must be retained in the medical record or research file.

9.4 Changes in the Protocol

Once the protocol has been approved by the UCSF CHR, any changes to the protocol must be documented in the form of an amendment. The amendment must be signed by the Investigator and approved by PRC and the CHR prior to implementation.

If it becomes necessary to alter the protocol to eliminate an immediate hazard to patients, an amendment may be implemented prior to CHR approval. In this circumstance, however, the Investigator must then notify the CHR in writing within five (5) working days after implementation. The Study Chair and the UCSF study team will be responsible for updating any participating sites.

10 Protection of Human Subjects

Appendix 1 Performance Status Criteria

ECOG Performance Status Scale		Karnofsky Performance Scale	
Grade	Descriptions	Percent	Description
0	Normal activity Fully active, able to carry on all pre-disease performance without restriction	100	Normal, no complaints, no evidence of disease
		90	Able to carry on normal activity; minor signs or symptoms of disease
1	Symptoms, but ambulatory Restricted in physically strenuous activity, but ambulatory and able to carry out work of a light or sedentary nature (e.g., light housework, office work)	80	Normal activity with effort; some signs or symptoms of disease
		70	Cares for self, unable to carry on normal activity or to do active work
2	In bed < 50% of the time Ambulatory and capable of all self-care, but unable to carry out any work activities Up and about more than 50% of waking hours	60	Requires occasional assistance, but is able to care for most of his/her needs
		50	Requires considerable assistance and frequent medical care
3	In bed > 50% of the time Capable of only limited self-care, confined to bed or chair more than 50% of waking hours	40	Disabled, requires special care and assistance
		30	Severely disabled, hospitalization indicated Death not imminent
4	100% bedridden Completely disabled Cannot carry on any self-care Totally confined to bed or chair	20	Very sick, hospitalization indicated Death not imminent
		10	Moribund, fatal processes progressing rapidly
5	Dead	0	Dead

Appendix 2 Schedule of Study Procedures and Assessments

Schedule of Study Procedures and Assessments						
Period/ Procedure	Screening	Imaging day 1	1-3 day post imaging	Follow-up survey 1	Follow-up survey 2	Clinical/imaging follow-up
Study day / Visit day	-30 to 1	1	2-4	2 – 30 days	Six months	3-12 months
Informed consent	X					
Laboratory values, history from medical record	X					
Pre-survey	X					
Performance status	X					
Blood pressure, HR	X					
Imaging Procedure						
⁶⁸ Ga-PSMA-11		X				
PET/CT or PET/MRI		X				
Follow-up						
Adverse event reporting			X			
Post-survey				X	X	
Clinical follow-up						X
Follow-up imaging						X*

* in patients who do not have biopsy proof or other criteria to qualify disease, repeat imaging 3-12 months after initiation of treatment or imaging will be performed

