e) Patient follow-up: Patients will be contacted one to three days after ^{68}Ga -PSMA-11 PET to assess for the development of delayed adverse events. Patients will be seen in the clinic if there are any concerning study related adverse events requiring further evaluation. Patients will also be followed up clinically and using conventional imaging for up to 12 months after ^{68}Ga -PSMA-11 PET. Follow-up imaging will be performed as allowed under standard of care.

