6.1.1.1 Screening Assessments

The Screening procedures and assessments must be completed within 30 days of the day 1 Visit.

- Laboratory values: all patients must have a recent PSA (within 30 days prior to study enrollment) consistent with BCR
 - If only one PSA greater than or equal to 0.2 ng/dL post radical prostatectomy is available, then a second confirmatory PSA must be checked prior to the ⁶⁸Ga-PSMA-11 PET study.
- Pathology: all patients must have histopathology/biopsy of the prostate with a documented Gleason score
- Performance status: all patients must have their Karnofsky performance status (or ECOG/WHO equivalent) evaluated (Appendix 1).
- Change in management: A pre-imaging survey of planned clinical management will be performed prior to ⁶⁸Ga PSMA-11 PET/CT imaging.

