6.1.3 Post-treatment Follow Up Visits

Patients will be followed for 1-3 days after enrollment, by phone. The following procedure will be performed:

- Evaluation of adverse events

Additionally, the following post-treatment follow up will be performed:

- Change in management: A post-imaging survey of clinical management using PSMA-11 PET/CT information will be performed ≤ 30 days of PSMA-11 PET/CT imaging for assessment of change in clinical management.

- Change in management 6 months post imaging: A survey of clinical management will be performed approximately 6 months after the PSMA-11 PET/CT imaging for assessment of change in clinical management.
- Conventional imaging follow-up 3-12 months post imaging: Conventional imaging follow-up shall be performed as per institutional standard of care. DICOM images /or associated report should be collected for analysis.

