 - For patients undergoing systemic treatment (alone or in combination with targeted treatment): If on post-treatment follow-up imaging within 3-12 months, lymph nodes seen on CT or MRI decrease by more than 30% in short axis diameter and PSA declines by more than 50%.

- If PSA increases by more than 50% on systemic therapy, then a increase in the size of lesion by more than 20% will be considered a true positive lesion.
- In subjects with localized suspected lymph node(s) receiving targeted treatment without concomitant systemic treatment there are two ways to meet true positive disease:
- If the subject shows a decrease of PSA by greater than 50% after targeted treatment and the lymph node does not enlarge (change in size less than 20% or less than 3 mm increase in short axis diameter) [OR]
 - If on post-treatment follow-up imaging within 3-12 months, lymph nodes seen on CT or MRI decrease by more than 30% in short axis diameter (with a minimum of 3 mm in change in size)
- For untreated patients: If on follow-up imaging within 3-12 months, lymph nodes seen on CT or MRI increase by more than 20% in short axis diameter (with a minimum of 3 mm in change in size).
- (2) False positive:
- For patients undergoing systemic treatment (alone or in combination with targeted treatment): If on post-treatment follow-up imaging within 3-12 months, lymph nodes seen on CT or MRI increase by more than 20% in short axis diameter and PSA decreases by more than 50%.
- In subjects with localized suspected lymph node(s) receiving targeted treatment without concomitant systemic treatment there are two ways to meet false positive disease:
- If the subject does not demonstrate a decrease of PSA by greater than 50% after targeted treatment [OR]
 - If on post-treatment follow-up imaging within 3-12 months, lymph nodes seen on CT or MRI increase by more than 20% in short axis diameter (with a minimum of 3 mm in change in size)
- For untreated patients: If on follow-up imaging within 3-12 months, lymph nodes seen on CT or MRI decrease by more than 30% in short axis diameter (with a minimum of 3 mm in change in size).
- (3) If all regions in a patient/region do not meet criteria for either True positive or False positive disease, then the patient/region will be considered inevaluable for primary endpoint.
- ii) Visceral lesions (non-lymph node soft tissue or organ) will be assessed by change in size. ⁶⁸Ga-PSMA-11 positive visceral lesions will be considered:
- (1) True positive:

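### Fifteen of the 35 follow-up routes in 8.3.2 b) need a post-PET PSA that the protocol never schedules, and after targeted treatment a missing PSA literally meets the false-positive rule

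*Combined protocol and SAP*

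**What the plan says.** **What is scheduled.** The one PSA that the protocol instructs sites to have is before the scan: "all patients must have a recent PSA (within 30 days prior to study enrollment) consistent with BCR" (6.1.1.1), with a confirmatory value, also before the scan, for some prostatectomy patients. In Appendix 2 the only laboratory row, "Laboratory values, history from medical record", is marked under screening and nowhere else. Section 6.1.3 lists adverse events, two management surveys and imaging after the scan. On imaging it says "Conventional imaging follow-up shall be performed as per institutional standard of care" and asks for the images or reports to be collected; it does not mention PSA. Section 5.1.1.2 adds "Patients will also be followed up clinically and using conventional imaging for up to 12 months after" the PET, and Appendix 2 has a Clinical follow-up row at 3-12 months. Neither says what clinical follow-up consists of.

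**What the reference standard needs.** Section 8.3.2 b) uses PSA change for all four lesion types. For nodes on systemic treatment, a true positive requires that they "decrease by more than 30% in short axis diameter and PSA declines by more than 50" per cent. For nodes given targeted treatment alone, one of the two false-positive rules is "If the subject does not demonstrate a decrease of PSA by greater than 50% after targeted treatment [OR"]. Visceral and prostate-bed lesions have the same rule. Bone has it with the added condition that treatment was of curative intent. The inevaluable category is reserved for findings that meet neither the true-positive nor the false-positive criteria.

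**The concern.** The rules that decide whether a PET finding is true or false rely on a measurement that the schedule does not name, time or ask sites to return. That alone would invite uneven data across centres in a study meant to support pooling for a marketing application (1.1).

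The larger difficulty is that the gap is not neutral. The targeted-treatment false-positive bullets are worded in the negative, so the absence of evidence of a PSA fall satisfies them as written. An unmeasured response is then scored as a failed one. Because the false-positive criterion has been met, the inevaluable category does not catch the case. At stake are the PPV estimates and, less directly, the number of true positives that enter sensitivity.

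**Working it through.** The plan gives no figure on this point to reproduce. The check is a count of the rules, a comparison with the schedule, and an illustration on assumed inputs.

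**1. Count.** Each bullet or OR branch in 8.3.2 b) i) to iv) is one route. Entries are routes needing a post-PET PSA change / all routes.

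| Lesion type | True positive | False positive | Both |
|---|---|---|---|
| Lymph nodes | 3/5 | 2/4 | 5/9 |
| Visceral | 3/5 | 2/4 | 5/9 |
| Bone | 1/7 | 1/2 | 2/9 |
| Prostate bed | 1/4 | 2/4 | 3/8 |
| Total | 8/21 | 7/14 | 15/35 |

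15/35 = 42.9%. If the sub-bullets on rising PSA under systemic therapy (one for nodes, one for visceral lesions) are folded into their parent routes, the count is (15 − 2)/(35 − 2) = 13/33, and nothing else changes. This is a share of rules, not of patients.

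**2. What happens when no post-PET PSA is recorded.**

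- *Targeted treatment without systemic treatment.* The PSA true-positive route cannot be met. The PSA false-positive route is met on a literal reading. There are four such bullets, one per lesion type.
- *Systemic treatment, nodes and visceral lesions.* All three routes for each (two true positive, one false positive) include a PSA condition, so none can be scored.
- *Systemic treatment, prostate bed.* The true-positive route uses size alone and the false-positive route needs PSA. Here a missing PSA can only remove false positives, which runs the other way.
- *Untreated nodes, visceral and prostate-bed lesions.* No route uses PSA.

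**3. Illustration for PPV.** A true positive relabelled false positive stays in the denominator (all scored positives), so

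PPV after = PPV × (1 − s × m),

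where s is the share of true positives confirmable only by PSA after targeted treatment and m is the fraction of those with no PSA recorded. Both are assumptions; the documents give neither. For the starting value I use 0.87, the first cohort's biopsy figure in 8.2.1. The plan calls it specificity, but reports no true negatives on biopsy, so it is read here as a PPV.

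- s = 0.20, m = 0.25: 0.87 × 0.95 = 0.83
- s = 0.20, m = 0.50: 0.87 × 0.90 = 0.78
- s = 0.10, m = 0.10: 0.87 × 0.99 = 0.86
- s = 0.30, m = 0.50: 0.87 × 0.85 = 0.74

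**4. Illustration for sensitivity.** False positives are not in the formula TP/(TP + FN); only the lost true positives matter. Take 70 true positives and 30 false negatives, which is the hypothesised 70%, and hold false negatives fixed:

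- 5% of true positives lost: 66.5/(66.5 + 30) = 68.9%
- 10% lost: 63/(63 + 30) = 67.7%

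**The case against.** The best defence is that clinical follow-up naturally includes PSA. Sections 8.3.2 b) and d) treat clinical follow-up as a source of evidence, and PSA is the only non-imaging, non-pathology response measure in those rules. Men with biochemical recurrence are likely to have PSA tests in routine care. The case report form is not in the documents, and the surveys in Appendix 3 appear only as a heading, so they may capture some treatment data. This stands to the extent that one cannot infer that post-PET PSA will be unavailable. The supportable statement is that it is not specified or scheduled, and that collection is left to each site's interpretation.

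A second defence is that the negative wording presupposes a measured PSA, that every lesion type has an inevaluable category, and that 8.3.2 d) calls the criteria a guide from which investigators may depart if they record it. A sensible reader might well apply the rule that way. But no rule for a missing PSA is stated, the literal text gives the opposite result, and case-by-case departure is a poor substitute for a rule in a reference standard.

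A third is that most confirmed disease is protected. This is largely right. A reader might infer that confirmed disease is turned into false positives; the documents do not support that. Pathology outranks follow-up. A patient with one true-positive region stays true positive when other regions are false positive on follow-up only. A true-positive lesion also outranks a follow-up false-positive lesion in the same region. Nodes, visceral and prostate-bed lesions have a size-only true-positive route after targeted treatment, and bone has six imaging routes. What remains unresolved is a single lesion that meets such a route and has no PSA: it satisfies both definitions, and no precedence within a lesion is given.

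**Conclusion.** The point holds in a limited form. The count of 15 in 35 and the absence of any specified post-PET PSA follow directly from the text. The false-positive default follows from a literal reading. It is confined to targeted treatment without systemic treatment (curative intent for bone) and bites on lesions whose only possible confirmation is PSA. For systemically treated nodes and visceral lesions the consequence is that follow-up cannot score them.

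The direct effect of the default is downward bias in PPV, a secondary endpoint. The effect on the primary sensitivity is indirect. A reader might also infer that the 375 verified patients, and so the power, are reduced. The documents do not show that: 8.2.1 defines the 375 by having imaging or biopsy follow-up, and a patient relabelled false positive is still among them. Any loss of information through inevaluable lesions cannot be quantified from the documents.

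The size depends on how many PSAs go unrecorded and how many lesions rest on PSA alone. The PPV range of 0.86 to 0.74 is an illustration on assumed inputs, not an estimate. The change is worth making because the direction of the default is predictable and the remedy is cheap.

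**What to change.** 1. In 6.1.3 and in the Clinical/imaging follow-up column of Appendix 2, list PSA values with dates, abstracted from the medical record through the 3-12 month follow-up. Add type and start date of treatment where the surveys do not already capture them.
2. In 8.3.2 b), reword the four targeted-treatment false-positive bullets along these lines: a PSA measured after targeted treatment shows no decrease of more than 50%. Keep the curative-intent condition for bone.
3. State that a missing PSA makes a PSA-dependent route not assessable, and that the lesion is inevaluable if no other route applies. For bone, check this against the residual false-positive bullet, which covers lesions that meet no true-positive criterion despite appropriate imaging; it would still apply.
4. State which result prevails when one lesion meets both a true-positive and a false-positive definition.

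The cost is about one page of chart abstraction and a few lines of text, with no added blood draw or visit. The downside is that some patients without a recorded PSA become inevaluable by that route; their number should be reported.

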Gallium-68 PSMA-11 PET in patients with biochemical recurrence

Study Drug: Gallium-68 PSMA-11

Version Date: 08/27/2017

NCT# 03353740

Abstract

Title	Gallium-68 PSMA-11 PET in patients with biochemical recurrence
Patient population	
 • Rising PSA after definitive therapy with prostatectomy or radiation therapy (external beam or brachytherapy): 
 ○ Post radical prostatectomy (RP) – AUA recommendation 
 ▪ PSA greater than or equal to 0.2 ng/mL measured more than 6 weeks after RP. ○ Post-radiation therapy – ASTRO-Phoenix consensus definition 
 ▪ Nadir + greater than or equal to 2 ng/mL rise in PSA
Rationale for Study	Gallium-68 PSMA-11 has been shown to have a higher sensitivity for the detection of metastatic prostate cancer compared to choline based imaging.
Primary Objective	
 • Sensitivity on a per-patient and per-region-basis of ⁶⁸Ga-PSMA-11 PET for detection of tumor location confirmed by histopathology/biopsy, clinical and conventional imaging follow-up.
Secondary Objectives	
 • PPV on a per-patient and per-region-basis of ⁶⁸Ga-PSMA-11 PET for detection of tumor location confirmed by histopathology/biopsy, clinical and conventional imaging follow-up. • Sensitivity and positive predictive value (PPV) on a per-patient and per-region basis of ⁶⁸Ga-PSMA-11 PET for detection of tumor location confirmed by histopathology/biopsy. • Detection rates on a per-patient basis of ⁶⁸Ga-PSMA-11 PET stratified by PSA value (0.2 - <0.5, 0.5 - <1.0, 1.0 - <2.0, 2.0 - <5.0, ≥5.0). Detection rate will be stratified by history of prostatectomy, radiation or both; as well as by whether the patient is on androgen deprivation therapy (ADT). • Impact of ⁶⁸Ga-PSMA-11 PET on clinical management in BCR patients. • Inter-reader reproducibility. • Safety of ⁶⁸Ga-PSMA-11 administration as categorized by CTCAE 4.03.
Study Design	This is a phase 3 multi-center open label study.
Number of patients	Total population of patients will be 1,500 patients across all institutions.

Duration of Therapy	The study will involve a single imaging study.
Duration of Follow up	The patients will be followed-up by phone one day after the study completion, and clinical and imaging follow-up will last for up to 12 months after the PSMA-11 PET study..

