3.4 Duration of Follow Up

Patients will be followed for one day after the administration of the radiopharmaceutical.

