- i) Lymph nodes will be considered positive if the ^{68}Ga -PSMA-11 uptake is focal and greater than blood pool (adjacent or mediastinal blood pool).
 - (1) Lymph nodes will be classified further by region: pelvic, retroperitoneal, thoracic, other. Additionally, pelvic lymph nodes will be subclassified according to their localization as follows: R/L obturator, R/L external iliac, R/L internal iliac and other (total of 7 subgroups). These regions will not be used for evaluation of the primary or secondary endpoints, but for exploratory analysis.
- ii) Visceral lesions will be considered positive if the ^{68}Ga -PSMA-11 uptake is focal and greater than physiologic background activity of the involvement organ or anatomic site.
 - (1) Visceral lesions will be classified further by major organ: lung, liver, other tissue. These regions will not be used for evaluation of the primary or secondary endpoints, but for exploratory analysis.
- iii) Bone lesions will be considered positive if the ^{68}Ga -PSMA-11 uptake is focal and greater than physiologic bone marrow.
 - (1) Bone lesions will be classified by further by region: spine, ribs, pelvis, extremities, skull, sternum, clavicle. These regions will not be used for evaluation of the primary or secondary endpoints, but for exploratory analysis.
- iv) Prostate bed and prostate lesions will be considered positive if the ^{68}Ga -PSMA-11 uptake is focal and greater than physiologic background activity of the involvement organ or anatomic site.

Reference Standard Definition

b) Follow-up Imaging:

All patients will be followed up 3-12 months with conventional imaging (dedicated CT, MRI and/or bone scan). Interpretation of follow-up imaging will be performed by local read. For lesions that are reported in the blinded reads but not reported in the local evaluation of follow-up imaging, the local readers will be informed of the location of the lesions and follow-up will be performed for these additional lesions. Preferably, the follow-up conventional imaging should be the same modality/modalities as the initial staging work-up to allow for reproducible and accurate comparisons.

^{68}Ga -PSMA-11 PET validation based on follow-up imaging:

- i) Lymph nodes will be assessed by change in size. ^{68}Ga -PSMA-11 positive lymph nodes will be considered:
 - (1) True positive:

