- (2) True negative patient: in the absence of True Positive or False Positive lesions, a patient will be considered a True Negative if there is pathology that is negative for disease and corresponding lesion is negative by PSMA PET.
 - (3) False positive patient:
 - (a) Pathology confirms a false positive lesion that is read as positive on PSMA PET.
 - (b) In the absence of pathology: there are no true positive regions, and there is a region that is categorized as false positive based on imaging or clinical follow-up.
 - (4) False negative patient: in the absence of True Positive or False Positive lesions, a patient will be considered a False Negative if there is pathology that is positive for disease and corresponding lesion is negative by PSMA PET. Additionally, patients without evidence of disease on PSMA PET but with biochemical evidence of disease will be considered a False Negative.
- ii) Region level evaluation: Each patient will have four evaluable regions (Table 1: prostate bed, pelvis, extrapelvic soft tissue, and bone metastases). Each region will be categorized as true positive or false positive as described above. Regions without evidence of PSMA positive disease or deemed inevaluable will not be included in the analysis.
 - (1) True positive region:
 - (a) Pathology confirms a PSMA avid lesion as a true positive in the region.
 - (b) In the absence of pathology, clinical or imaging follow-up demonstrates a true positive lesion within the region independent of the presence of an inevaluable lesion or a false positive lesion
 - ie true positive disease will supersede a false positive lesion in the region based analysis if based on imaging/clinical follow-up
 - (2) True negative region: in the absence of True Positive or False Positive lesions within a region, the region will be considered a True Negative if there is pathology that is negative for disease in the region and corresponding lesion is negative by PSMA PET.
 - (3) False positive region:
 - (a) Pathology confirms a PSMA avid lesion as a false positive in the region

- (b) In the absence of pathology, there are no true positive lesions in the region, and there is a false positive lesion by clinical or imaging follow-up.
- (4) False negative region: in the absence of True Positive or False Positive lesions in a region, the region will be considered a False Negative if there is pathology that is positive for disease in the region and corresponding lesion is negative by PSMA PET.

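### The plan gives conflicting rules on who has follow-up imaging, and the Appendix 2 condition is set per patient although a primary endpoint is per region

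*Combined protocol and SAP*

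**What the plan says.** **Who is imaged.** Section 8.3.2, under b) Follow-up Imaging, covers everyone: "All patients will be followed up 3-12 months with conventional imaging". Section 5.1.1.2 e) ties it to routine practice: "Follow-up imaging will be performed as allowed under standard of care". Section 6.1.3 does the same, "Conventional imaging follow-up shall be performed as per institutional standard of care", and asks that images or reports be collected. The Appendix 2 schedule puts an asterisk on the follow-up imaging row, and its footnote limits the requirement: "in patients who do not have biopsy proof or other criteria to qualify disease, repeat imaging 3-12 months". The clinical follow-up row has no asterisk.

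**For how long.** Section 3.4 reads: "Patients will be followed for one day after the administration of the radiopharmaceutical". The Abstract says "clinical and imaging follow-up will last for up to 12 months after the PSMA-11 PET study", and Section 5.1.1.2 e) says "Patients will also be followed up clinically and using conventional imaging for up to 12 months after" the PET.

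**What the labels are needed for.** Section 2.1 makes sensitivity primary both per patient and per region. Section 8.3.2 d) ii) says "Each patient will have four evaluable regions" and leaves inevaluable regions out of the analysis. Under 8.3.2 d) i), one true-positive region is generally enough to make the patient a true positive, unless pathology shows a false positive elsewhere.

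**The concern.** The footnote's condition suits the per-patient label, which one confirmed lesion broadly settles. It does not suit the per-region label, because each PET-positive region needs its own verification. Take a man with a biopsy-proven pelvic node and further PET-positive extrapelvic nodes. Under the footnote he is no longer in the group for whom repeat imaging is required. If no routine scan or PSA response labels the second region, it becomes inevaluable and leaves the per-region analysis.

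Whether a region is verified would then depend partly on whether another region in the same man had already been confirmed. Regional sensitivity and PPV would rest on a selected set of regions and lose precision. Sites working from different sections would also verify differently, in data that Section 1.1 says are to be pooled for an NDA.

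**Working it through.** **1. The rules side by side.**

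| Place | Who is imaged | Until when |
|---|---|---|
| Abstract | not specified | up to 12 months |
| 3.4 | not specified | one day |
| 5.1.1.2 e) | as standard of care allows | up to 12 months |
| 6.1.3 | per institutional standard of care | 3-12 months |
| 8.3.2 b) | all patients | 3-12 months |
| Appendix 2 footnote | only patients not yet qualified | 3-12 months |

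Only 3.4 conflicts on duration. On who is imaged there are three rules. Section 8.2.1 expects roughly 15 to 20% of patients to have imaging follow-up, so the all-patients wording is not what the sample size assumes.

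**2. The plan's own figure.** Inputs from Section 8.2.1: null 0.50, alternative 0.70, one-sided alpha 0.01, power 90%, regional prevalence 20%.

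n = [2.326 × √(0.5 × 0.5) + 1.282 × √(0.7 × 0.3)]² / 0.2² = 76.6, so 77. The plan states 75, which is close enough to count as reproduced. Then 75 / 0.20 = 375 verified patients, and 375 / 1,500 = 25%.

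**3. What a loss per region would do.** Approximate power = Φ{[0.2√n − 2.326 × 0.5] / √0.21}. To keep 75 per region, 375 / (1 − loss) verified patients are needed. The loss shares are assumptions, because the documents give none.

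| Share of the 75 not verified | n | Approximate power | Verified patients needed to keep 75 |
|---|---|---|---|
| 0% | 75 | 89% | 375 |
| 5% | 71 | 87% | 395 |
| 10% | 68 | 86% | 417 |
| 20% | 60 | 80% | 469 |
| 30% | 52 | 73% | 536 |
| 40% | 45 | 65% | 625 |

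If the other regions are in fact verified, the loss is zero and 75 / 375 / 1,500 stand.

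**4. Direction for regional sensitivity.** Under 8.3.2 d) ii), a region-level false negative can come only from pathology. Missing follow-up imaging therefore removes no false negatives, but it can remove true positives. With assumed counts of 70 true positives and 30 false negatives, sensitivity is 70/100 = 70%. Losing 20% of the true positives leaves 56/(56 + 30) = 65%. The table in step 3 holds sensitivity at 70% and does not include this shift. For regional PPV the documents do not fix a direction.

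**The case against.** The strongest reply is that the footnote says less than it might seem to. A reader might infer that the schedule halts imaging for the whole man once one lesion is confirmed and leaves his other regions unverified. The text does not say that. The footnote limits a requirement; it does not forbid or stop imaging. Section 6.1.3 still calls for standard-of-care imaging and collection of images or reports, with no exception for confirmed men. Sections 8.1.2 and 8.3.2 b) tell local readers where the PET-positive lesions are. Bone can qualify on baseline CT, bone scan or MRI, and a PSA fall after targeted treatment can label a lesion. All of this stands, and it is why the other regions may, rather than will, stay unverified.

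A reader might also infer that a site following 3.4 would collect almost no reference standard. That site would have to ignore the Abstract, 5.1.1.2 e), 6.1.3, 8.3.2 b) and Appendix 2. Section 3.4 most plausibly means safety contact.

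A third tempting step is a head count: 0.19 × 1,500 = 285 biopsied men, of whom an assumed 20-40% have a second positive region, giving 57-114 men lost against a requirement of 75. The documents do not support it:

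- The 19% is the first cohort's biopsy rate, and Section 8.2.1 expects it to fall.
- At the anticipated 15-20% imaging rate, only 57 × 0.15 ≈ 9 to 114 × 0.20 ≈ 23 men would lose an imaging label.
- The count runs over four regions, while 75 is per region. Spread evenly, 9-23 is about 2-6 per region (n = 73 to 69, power 88% to 86%). Even the undiscounted 57-114 is about 14-29 per region (n = 61 to 46, power 81% to 66%).
- The shares in Section 8.2.1 sum to 15 + 27 + 24 + 11 + 24 = 101% with PET-negative men included. They look like one category per man and give no multi-region rate.

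Finally, the success criterion in 8.3.2 is per patient, and the footnote broadly serves it. That also stands. None of these replies says which imaging rule governs, or whether the footnote applies by patient, region or lesion.

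**Conclusion.** The point holds as an unresolved conflict with a mismatch of unit. Three rules on who is imaged must be reconciled, the one-day statement in 3.4 needs its scope stated, and a per-patient condition does not secure verification for a per-region primary endpoint. The effect is possible selective verification and lost precision in regional sensitivity and PPV, with a tendency to lower regional sensitivity if imaging-verified true positives are lost. The per-patient success criterion is less exposed.

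The size cannot be derived, since no multi-region share is given and the biopsy rate is expected to change. The losses and powers shown are scale only. They omit men qualified at baseline by criteria other than biopsy.

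Two assumptions matter. The primary reference standard is taken as pathology plus imaging and clinical follow-up, as in 2.1 and 8.3.2, although 8.3.1 mentions histopathology alone. Region-level false negatives are taken to count, as 8.3.2 d) ii) defines them, although the same section sets aside regions without PSMA-positive disease.

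**What to change.** Reconcile Sections 3.4, 5.1.1.2 e), 6.1.3, 8.3.2 b) and Appendix 2 into one rule:

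- Label 3.4 as safety follow-up, if that is what is meant.
- State that conventional imaging done up to 12 months after the PET is collected for every scanned patient, whether or not a lesion is already confirmed.
- State the footnote's condition per PET-positive region instead of per patient.
- Keep regions still unlabelled at 12 months as inevaluable, and report their number by region and by whether another region in the same man was already confirmed.

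The last item lets a reader judge how selective the verification was. A rule that follow-up continues until every region has a label should not be written, because it could not be met without added scans.

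The cost is protocol wording and retrieval of existing images or reports for men with one confirmed lesion. With imaging itself left to standard of care, no scans or readers are added.
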